## 3. Study Procedures

### a. Study design, including the sequence and timing of study procedures

This is a prospective, randomized, unblinded, controlled study in the Harriet Lane Clinic (HLC), the Johns Hopkins Children's Center pediatric primary care resident teaching practice and the Johns Hopkins Children's Center Pediatric Emergency Department (Peds ED). The HLC has clinics for acute care (e.g., sick visits) and continuity (e.g., well child and follow-up visits). We will purchase Cellsopes, iPhones, phone cases, and locking storage systems for each setting. There will be no direct collaboration between the study investigators and Cellscope related to this study. We will evaluate the above aims by block-randomizing in 2-week blocks: 1 week where the Cellscope will be available and 1 week where only traditional otoscopy will be available. Because residents rotate through the HLC and Peds ED in 2 and 4-week rotations, this will allow for the inclusion of the same trainees in each arm to act as their own control and ensure there is no use of the Cellscope during the traditional-only weeks. During Cellscope weeks, the traditional direct otoscopes will be available based on trainee/supervisor preference. During the traditional weeks, the Cellscope will not be available, thus the standard of care will not be changed during our study. iPhones will be secured with 6-digit numeric passcodes, in compliance with JHMI security standards. Recordings/images of external and middle ear structures will be obtained in a HIPAA compliant manner without collecting any PHI.

During Cellscope weeks, trainees and supervisors will be given access to the Cellscope and asked to use this tool for their otoscopic exams (research procedure). They will have full discretion of when an otoscopic examination is indicated, based on their existing practice and standard of care. We will then ask that the

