trainees and supervisors each fill out an index card survey to record the following outcomes: agreement between trainee and supervisor using the OMgrade scale (validated otitis media diagnostic tool), trainee confidence in exam, antibiotic prescription, need for conversion to traditional otoscopy, and whether a repeat exam was obtained. During the traditional weeks, the Cellsopes will be unavailable, locked in an enclosure, and traditional otoscopy (routine care) will be the only method available. The same index card survey will be completed by the trainees and supervisors. There will be no change to patient restraint, as described above.

b. Study duration and number of study visits required of research participants.

The study will last for between 9-12 months depending on the number of patients enrolled. Only one study visit is required per research participant. The same patient will be able to be included in the study multiple times if they present to the HLC or Peds ED on multiple occasions.

c. Blinding, including justification for blinding or not blinding the trial, if applicable.

This study will be unblinded. It is not possible to perform this study in a blinded manner given the obvious difference in the handheld hardware.

d. Justification of why participants will not receive routine care or will have current therapy stopped.

Standard of care is traditional direct otoscopy, as described above. We are using an equivalent method of otoscopy that allows the identical visualization of the external and middle ear structures. It will also be explicitly stated to providers that they can revert to traditional otoscopy if they feel that the Cellscope is not able to identify the needed structures.

e. Justification for inclusion of a placebo or non-treatment group.

N/A

f. Definition of treatment failure or participant removal criteria.

If any provider feels that the Cellscope is not able to appropriately identify the needed ear structures, that will be considered a failure of the Cellscope, and that provider will be able to immediately revert to a traditional otoscope. Furthermore, patients and guardians may opt for providers to use the traditional otoscope at any time. This will be tracked.

g. Description of what happens to participants receiving therapy when study ends or if a participant's participation in the study ends prematurely.

Resumption of traditional care, without any harm to the patient.

h. Informed Consent

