If patients are interested in participating the trainees or supervisors will obtain informed verbal consent from the parent or legal guardian of the patient prior to examining the child. Explaining the study, obtaining consent, answering questions, and assessing parent and patient understanding is expected to take under 5 minutes, which is typical for a similar conversation clinical setting. A copy of the IRB protocol will be provided upon request. A waiver of written consent is requested because the consent document is the only record linking the subject and the research. The research presents no more than minimal risk of harm to subjects and involves no procedures for which written consent is normally required outside of the research context.

i. Provider Training

Providers will be trained on setting up the Cellscope: attaching the case to the iPhone, attaching the Cellscope to the case, turning on the iPhone and unlocking it. They will also be trained on how to use the Cellscope application to record non-PHI containing images/videos. This training will be done by members of the study team who are proficient in using the device and app. This will occur in whatever clinical setting, in which they are assigned (Pediatric Emergency Room, Harriet Lane Acute Clinic, Harriet Lane Continuity Clinic). This will take place prior to them using the device on any patients for the purposes of this study or any other indication.

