#### 4. Inclusion/Exclusion Criteria

**Inclusion:**

- All trainees and supervisors
- All patients where otoscopy would traditionally be indicated, at the discretion of the clinical team
  - All ages included

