**5. Study Statistics**

a. Primary outcome variable.

Aim 1:

- A. Inter-rater reliability between trainee and supervisor utilizing the OMgrade scale

Aim 2:

- A. Rates of patients who receive antibiotics

- B. Levels of provider confidence in exam based on a standardized confidence measure

Aim 3: Rate of repeat exams by supervisors with and without Cellscope

b. Secondary outcome variables.

Aim 4: Rate of provider decided use of traditional otoscopy during Cellscope weeks

c. Statistical plan including sample size justification and interim data analysis.

Descriptive statistics will be performed to analyze our outcome measures in conjunction with Johns Hopkins BEAD Core statisticians.

1. Calculation of descriptive statistics such as mean, median, SD, range will be employed.
2. Examination of graphs such as outcome vs. time, scatterplots of two variables, Kaplan-Meier curves.
3. Estimation of differences between two groups with comparison by t-test or Mann-Whitney test.
4. Estimation and testing of within-person changes by matched t-test or Wilcoxon signed-rank test.
5. Multiple linear regression, logistic regression, or Cox proportional hazards regression.
6. Repeated measures models (usually requires the help of a statistician).
7. Comparison of proportions by the determination of kappa values will be employed.
8. Sample size will be calculated with an alpha of 0.05 and power of 80% to detect a change of 10%.  
We will have a minimum sample size of 392 subjects based on this calculation.

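### Providers who know the week's arm decide who is examined and enrolled, and no case-mix variable is planned that could check the antibiotic comparison

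*Combined protocol and SAP*

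**What the plan says.** All references are to the Combined protocol and SAP.

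- **Allocation (3a).** The plan is "block-randomizing in 2-week blocks: 1 week where the Cellscope will be available and 1 week where only traditional otoscopy will be available". The second week of each block follows from the first.
- **Visibility (3a, 3c).** Section 3c states "This study will be unblinded". Section 3a adds: "During the traditional weeks, the Cellsopes will be unavailable, locked in an enclosure, and traditional otoscopy (routine care) will be the only method available". Every provider therefore knows the arm before a patient arrives.
- **Decision to examine (3a, 4).** "They will have full discretion of when an otoscopic examination is indicated, based on their existing practice and standard of care". That sentence stands in the paragraph on Cellscope weeks, but the inclusion criterion covers both arms: "All patients where otoscopy would traditionally be indicated, at the discretion of the clinical team". There are no exclusions, and all ages are included.
- **Consent (3h).** For interested families, "the trainees or supervisors will obtain informed verbal consent from the parent or legal guardian of the patient prior to examining the child".
- **Data collected (3a).** The listed card items are trainee-supervisor agreement, trainee confidence, antibiotic prescription, conversion to traditional otoscopy and repeat exam.
- **Outcomes and analysis (5a, 5c).** Outcome 2A is "Rates of patients who receive antibiotics". Aim 3 is "Rate of repeat exams by supervisors with and without Cellscope". Section 5c lists regression among several methods but names no covariates.

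**The concern.** Randomising weeks makes the weeks comparable in expectation. It does not do so for the patients picked within each week by people who know the arm. The settings run from well-child visits to the emergency department, so there is room for the mix to move. A new device with a screen could prompt looks into ears that would otherwise be left alone, or providers could approach different families in the two kinds of week.

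The analysed set supplies the denominator of outcome 2A. If Cellscope weeks held more low-suspicion children, the antibiotic rate would fall with prescribing unchanged. Aim 2 hopes for a fall, so the artefact could be read as success. With verbal consent, recordings without identifiers and no case-mix item listed for the card, the documents describe no route for recovering the mix afterwards.

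**Working it through.** **1. The plan's own figure.** Section 5c gives 392 subjects for alpha 0.05, 80% power and a change of 10%. It does not state the outcome, the base rate, whether the change is absolute or relative, or whether 392 is a total. The figure can be reached in more than one way. For 10% versus 20%, two-sided and unpooled, n per arm = (1.960 + 0.842)² × (0.10×0.90 + 0.20×0.80) / 0.10² = 196.2, or 392.4 in total. For 45% versus 55%, two-sided and pooled, it is 392 per arm. The point here does not depend on which is meant.

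**2. Dilution of the antibiotic rate with no device effect.** The documents give no antibiotic rates, so all inputs are assumptions: rate b = 30% in traditional weeks, extra Cellscope-week exams as a fraction e of the traditional-week number, and antibiotic rate l = 5% among the extra patients.

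Cellscope-week rate = (b + e×l) / (1 + e)

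| Extra exams e | Calculation | Rate | Shift (points) |
|---|---|---|---|
| 5% | (0.30 + 0.05×0.05)/1.05 | 28.8% | -1.2 |
| 10% | (0.30 + 0.10×0.05)/1.10 | 27.7% | -2.3 |
| 20% | (0.30 + 0.20×0.05)/1.20 | 25.8% | -4.2 |
| 50% | (0.30 + 0.50×0.05)/1.50 | 21.7% | -8.3 |

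Sensitivity at e = 20%: with l = 15% the shift is (0.30 + 0.20×0.15)/1.20 - 0.30 = -2.5 points; with b = 40% and l = 5% it is (0.40 + 0.20×0.05)/1.20 - 0.40 = -5.8 points. The sign can reverse. If Cellscope weeks instead dropped low-suspicion exams equal to 10% of the traditional number, the rate would be (0.30 - 0.10×0.05)/0.90 = 32.8%, a rise of 2.8 points.

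**3. The same bias as a false-positive rate.** Let a share π of enrolled patients have ear complaints, with antibiotics given to 40% of these and 5% of others, so the arm's rate is 0.40π + 0.05(1 - π). The difference between arms is 0.35 times the difference in π. Assume 196 independent patients per arm (392 read as a total), a two-sided 5% test, and π = 50% in one arm.

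| π in the other arm | Spurious difference (points) | Chance of a significant result |
|---|---|---|
| 45% | 1.75 | about 7% |
| 40% | 3.5 | about 14% |
| 30% | 7.0 | about 42% |

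**4. Agreement.** Dichotomise the OMgrade result and hold trainee sensitivity at 0.80 and specificity at 0.90 against the supervisor (assumed). With prevalence p, observed agreement is Po = 0.80p + 0.90(1 - p), the trainee's positive rate is q = 0.80p + 0.10(1 - p), chance agreement is Pe = pq + (1 - p)(1 - q), and kappa = (Po - Pe)/(1 - Pe). Kappa is 0.70, 0.71, 0.69, 0.65 and 0.53 at prevalence 50%, 40%, 30%, 20% and 10%. Case mix barely moves it until pathology is uncommon.

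**5. Repeat exams.** The rate uses the same selected patients, so it is exposed in principle. No size was calculated.

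**The case against.** The plan does contain anchoring language. Eligibility is tied to whether an ear exam would be called for under usual practice, and section 3a repeats the tie to routine care. Entry is meant to cover everyone who meets that test, with no exclusions, so enrolling only easy children would depart from the protocol. Families' interest also matters, so enrolment is not purely the provider's choice. The alternating weeks and shared trainees limit calendar and provider differences. Regression is among the listed methods, and the card itself is not reproduced.

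Much of this stands. It is why the documents show only that case mix can differ, not that it will. But the anchoring words state an intention without a check, and having the same trainees in both arms balances providers rather than patients. Listing regression does not say which patient characteristics it would adjust for, and none appears among the listed card items.

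A reader might infer that the larger shifts take up most of a 10-point antibiotic effect for which the trial is sized. The documents do not support that: section 5c ties its 10% change to no outcome and does not say whether it means percentage points.

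**Conclusion.** The concern holds as a gap in what is measured, chiefly for outcome 2A. Allocation is open, the same providers then control examination and consent, and neither a case-mix item nor a case-mix covariate is named. An observed antibiotic difference could therefore not be told apart from a different mix of patients.

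Its direction and size are unknown. With the assumed 30% and 5% rates the shift runs from about -1.2 points at 5% extra exams to -8.3 points at 50%, and it could run the other way. Nothing in the documents makes the upper end likely. The false-positive rates in the working also assume independent patients and 196 per arm.

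Two stronger readings are not supported. One is that the antibiotic result will be biased towards the device: the text permits differential selection but does not show it. The other is that all primary outcomes shift materially: the agreement effect is likely small unless pathology is uncommon, and the repeat-exam effect is possible but unquantified.

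**What to change.** 1. Add non-identifying tick boxes to the existing index card: age band, setting, and visit reason (ear symptoms or fever; other sick visit; well or follow-up visit).
2. Compare these by arm. Prespecify them as adjustment variables in the regression for outcome 2A and for the repeat-exam rate, and show agreement by visit reason as well as overall.
3. Report enrolled exams per week by arm against the aggregate weekly visit count for each setting, so that a change in examination or enrolment can be seen.

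The randomisation is unchanged. The cost is a slightly longer card, a short IRB wording change, one aggregate count per setting per week and a few model terms. The limit is that adjustment covers measured case mix only; differences in suspicion or cooperation within a visit reason remain.

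An antibiotic rate per clinic visit by randomised week is an optional further check, because its denominator does not depend on who was enrolled. It is worth adding only if aggregate weekly prescription counts are readily available: it needs data on non-enrolled patients and would include antibiotics given for conditions other than AOM.

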#### 4. Inclusion/Exclusion Criteria

**Inclusion:**

- All trainees and supervisors
- All patients where otoscopy would traditionally be indicated, at the discretion of the clinical team
  - All ages included

**Exclusion:**

- None

**5. Study Statistics**

a. Primary outcome variable.

Aim 1:

- A. Inter-rater reliability between trainee and supervisor utilizing the OMgrade scale

Aim 2:

- A. Rates of patients who receive antibiotics

- B. Levels of provider confidence in exam based on a standardized confidence measure

Aim 3: Rate of repeat exams by supervisors with and without Cellscope

b. Secondary outcome variables.

Aim 4: Rate of provider decided use of traditional otoscopy during Cellscope weeks

c. Statistical plan including sample size justification and interim data analysis.

Descriptive statistics will be performed to analyze our outcome measures in conjunction with Johns Hopkins BEAD Core statisticians.

1. Calculation of descriptive statistics such as mean, median, SD, range will be employed.
2. Examination of graphs such as outcome vs. time, scatterplots of two variables, Kaplan-Meier curves.
3. Estimation of differences between two groups with comparison by t-test or Mann-Whitney test.
4. Estimation and testing of within-person changes by matched t-test or Wilcoxon signed-rank test.
5. Multiple linear regression, logistic regression, or Cox proportional hazards regression.
6. Repeated measures models (usually requires the help of a statistician).
7. Comparison of proportions by the determination of kappa values will be employed.
8. Sample size will be calculated with an alpha of 0.05 and power of 80% to detect a change of 10%.  
We will have a minimum sample size of 392 subjects based on this calculation.

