## 2. Objectives

Aim 1: To establish whether a smartphone otoscope improves diagnostic accuracy of tympanic membrane (TM) pathology for trainees, compared to supervisor.

Aim 2: To determine whether smartphone otoscope improves diagnostic confidence of trainees, thereby reducing frequency of antibiotic prescriptions for AOM.

Aim 3: To determine whether there is a change in repeat exam rates by supervisors, comparing with/without Cellscope.

Aim 4: To determine whether trainees convert to traditional otoscope use during the weeks that Cellscope is available.

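### Aim 1 promises a conclusion on trainee diagnostic accuracy, but measures only agreement with a supervisor grade that is not obtained the same way in both arms

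*Combined protocol and SAP*

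**What the plan says.** Section 2 states Aim 1 as: "To establish whether a smartphone otoscope improves diagnostic accuracy of tympanic membrane (TM) pathology for trainees, compared to supervisor". Section 5a lists one outcome for it: "Inter-rater reliability between trainee and supervisor utilizing the OMgrade scale". Section 3a describes the data source. It asks that "trainees and supervisors each fill out an index card survey to record the following outcomes: agreement between trainee and supervisor using the OMgrade scale". No other reference for the true state of the ear, such as a masked expert reading, is named.

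Section 3a also fixes the instruments. In Cellscope weeks, "trainees and supervisors will be given access to the Cellscope and asked to use this tool for their otoscopic exams", while "the traditional direct otoscopes will be available based on trainee/supervisor preference". In the other weeks, "traditional otoscopy (routine care) will be the only method available".

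The card also records "need for conversion to traditional otoscopy, and whether a repeat exam was obtained". The rate of supervisor repeat exams is the Aim 3 outcome in Section 5a. Section 3d asserts: "We are using an equivalent method of otoscopy that allows the identical visualization of the external and middle ear structures". Section 3f provides for any provider who finds the Cellscope view inadequate.

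**The concern.** An accuracy claim needs a reference that is independent of the intervention, or at least obtained in the same way in both arms. Here the intervention reaches both members of the pair, because the trainee and the supervisor change device together. A difference in agreement between arms then mixes three things: a change in the trainee's accuracy, a change in the supervisor's accuracy, and a change in how far their errors coincide. Nothing in the statistical plan separates them.

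A second gap adds to this. Whether the supervisor looks in the ear again is itself compared between arms, so a supervisor's own examination cannot be assumed. The documents do not say what a supervisor who did not examine enters as a grade. They set no order for the two cards and no masking of one from the other.

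Followed as written, the study could report a gain, a loss or no change in trainee accuracy when the result reflects how the supervisor's grade was obtained.

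**Working it through.** **What the plan's figures give.** The plan states no expected agreement, kappa or accuracy, so there is no Aim 1 figure to reproduce. The only scale is Section 5c, item 8: alpha 0.05, power 80%, a change of 10%, minimum 392 subjects. With the usual two-sided constant 7.849, a 10-point absolute difference at maximum variance needs 2 × 0.25 × 7.849 / 0.01 = 392.4 per arm. At 80% vs 90% it needs (0.16 + 0.09) × 7.849 / 0.01 = 196.2 per arm, or 392.4 in total. The figure therefore fits a 10-point absolute change. However, the plan does not say which outcome or baseline it applies to, or whether 392 is per arm or in total.

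**Inputs for the illustration (all assumed).** The grade has two categories; sensitivity and specificity both equal accuracy; errors are independent. Trainee accuracy is T and supervisor accuracy is S, with S = 0.85 in traditional weeks. The proportion of abnormal ears is p.

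**Raw agreement.** Po = T × S + (1 − T) × (1 − S). With T the same in both arms, the shift is (2T − 1) × (S in Cellscope weeks − S in traditional weeks).

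With T = 0.75 in both arms:

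- S = 0.85: 0.75 × 0.85 + 0.25 × 0.15 = 0.675
- S = 0.95: 0.75 × 0.95 + 0.25 × 0.05 = 0.725, a shift of +5 points
- S = 0.75: 0.75 × 0.75 + 0.25 × 0.25 = 0.625, a shift of −5 points
- S changed by 2 points: 0.5 × 0.02 = 1 point; by 5 points: 0.5 × 0.05 = 2.5 points

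For T from 0.70 to 0.80, with S fixed at 0.85 in traditional weeks and 0.75 to 0.95 in Cellscope weeks, the extremes are ±0.60 × 0.10 = ±6 points.

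**Kappa (Section 5c, item 7).** Kappa = (Po − Pe) / (1 − Pe), where Pe = ab + (1 − a)(1 − b), a = pT + (1 − p)(1 − T) and b = pS + (1 − p)(1 − S). At p = 0.3 and T = 0.75, a = 0.40. For S = 0.85, b = 0.36 and Pe = 0.528, so kappa = 0.147 / 0.472 = 0.311.

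| p | S = 0.85 | S = 0.95 | S = 0.75 |
|---|---|---|---|
| 0.2 | 0.256 | 0.344 | 0.176 |
| 0.3 | 0.311 | 0.407 | 0.219 |
| 0.5 | 0.350 | 0.450 | 0.250 |

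The shifts are +0.09 to +0.10, or −0.08 to −0.10. At p = 0.3, changing S by 2 or 5 points moves kappa by about 0.02 or 0.05.

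**The reverse error.** Let T rise from 0.75 to 0.80. Agreement stays flat if (2 × 0.80 − 1)(2S − 1) = (2 × 0.75 − 1)(2 × 0.85 − 1) = 0.35, which gives S = 0.792. Agreement is then 67.5% and kappa (p = 0.3) 0.311 in both arms, and a real 5-point trainee gain is missed.

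**Grades that are not independent.** This route is inferred, because the plan does not say how such grades arise. Take T = 0.75 and S = 0.90, so independent errors give 0.70 agreement. If supervisors adopt the trainee's grade in an extra share s of Cellscope visits, agreement is 0.70 + 0.30s, or 73% at s = 0.10 and 82% at s = 0.40. If the raters' errors coincide for half of the possible excess, the probability that both are wrong is 0.025 + 0.5 × (0.10 − 0.025) = 0.0625. Agreement is then 1 − 0.25 − 0.10 + 2 × 0.0625 = 77.5%. Trainee accuracy is unchanged in each case.

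**The case against.** The best defence is that Aim 1 names the supervisor as comparator, so the plan openly measures trainees against supervisors. Comparing weeks with and without the device, with both providers using what is available, is a coherent pragmatic design. That stands as a defence of the agreement comparison. It does not support the word accuracy, because a comparator obtained differently by arm cannot carry that conclusion.

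It can also be said that no document states that supervisor accuracy depends on the device, that Section 3d calls the methods equivalent, and that a provider with a poor view may revert. The equivalence is asserted and not tested. It sits awkwardly beside an aim that asks whether the same device improves trainees' accuracy. Reversion would soften a loss of supervisor accuracy, and the illustrations give no credit for it. But it leaves a mix of devices in one arm and does nothing about a gain.

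The numerical objections are fair. Every input is assumed, the 5-point shift needs a 10-point change in supervisor accuracy, the flat case needs nearly exact cancellation, and two categories simplify the scale. A supervisor grading without looking is an inference, and the card itself is not in the documents. These points limit any claim about the likely size of the bias. They do not give the plan a way to tell the supervisor's contribution from the trainee's.

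**Conclusion.** The concern holds, and Aim 1 needs correcting as written. The text establishes the mismatch: an accuracy objective, agreement as its only outcome, and a supervisor instrument that differs by arm. Having the same trainees in both arms balances trainee skill but does not hold the supervisor's grade constant.

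The bias is possible, not expected, and can go in either direction. Under the stated assumptions it is about 1 to 2.5 points of agreement for modest device effects on supervisors and 5 to 6 points for a 10-point effect. Five points is half of the 10% design change, if that is read as percentage points of agreement. The conclusion rests on the mismatch and the undefined supervisor grade, not on these sizes.

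**What to change.** 1. Reword the Aim 1 objective and its planned conclusion as trainee agreement with the supervisor on OMgrade, with and without the Cellscope available. Drop the claim about diagnostic accuracy. This is the decisive change.
2. Have the trainee complete the OMgrade card before presenting the case, and have the supervisor complete theirs without seeing it. State that this protects the trainee's grade but does not make the supervisor's independent, because the case is presented verbally.
3. Extend the existing conversion and repeat-exam items so that the supervisor's card shows the source of the grade: own examination and which device, the trainee's recording, or the trainee's report.
4. Keep all pairs in the main analysis and report agreement by source and arm. Add a sensitivity analysis limited to pairs with the supervisor's own examination. State that this subset is selected after allocation and still differs in device between arms.

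Items 2 to 4 are disclosure and partial mitigation; they do not remove the device difference. The cost is some wording, one instruction on card order, the extension of two card items, slightly more card burden and a more modest conclusion. No extra reader or examination is needed, and no pairs leave the main analysis.

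### Aim 1 asks about trainee accuracy against the supervisor, but its only outcome is agreement, which cannot show the direction of trainee error and can hide a trade of over-calls for misses

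*Combined protocol and SAP*

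**What the plan says.** Section 2 words Aim 1 as: "To establish whether a smartphone otoscope improves diagnostic accuracy of tympanic membrane (TM) pathology for trainees, compared to supervisor". The documents give no other reference standard, so the supervisor's grade serves as the reference. Section 5a lists one outcome for this aim: "Inter-rater reliability between trainee and supervisor utilizing the OMgrade scale". Section 3a describes the recorded item as "agreement between trainee and supervisor using the OMgrade scale", taken from cards that trainee and supervisor each complete in both week types.

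The only agreement statistic in the plan is in Section 5c, item 7: "Comparison of proportions by the determination of kappa values will be employed". That item does not mention Aim 1 and gives no weights, so reading kappa as the Aim 1 analysis is a reasonable inference rather than a stated fact. Sensitivity, specificity, an over-call or missed rate, a test for a shift between the two raters, and an OMgrade cut-point are all absent. The regression and repeated-measures methods in items 5 and 6 are assigned to no aim.

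In Cellscope weeks, "trainees and supervisors will be given access to the Cellscope and asked to use this tool for their otoscopic exams". Section 5c, item 8 gives a minimum of 392 subjects (alpha 0.05, power 80%, a 10% change), without naming the endpoint or saying whether 392 is per arm or in total.

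**The concern.** Accuracy against a reference has a direction: a trainee can grade above the supervisor (over-call) or below (miss). An agreement coefficient with symmetric weights pools the two kinds of error. If the device made trainees more cautious, over-calls could fall while misses rise, and the Aim 1 result could look flat or even slightly better. If it made them readier to call disease, the reverse could happen. These are different answers to the question Aim 1 poses, and the planned outcome does not separate them.

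**Working it through.** **Plan's own figure.** 392 is reproduced as a per-arm number by the maximum-variance form: 2 × 0.25 × (1.96 + 0.84)² / 0.10² = 0.5 × 7.84 / 0.01 = 392. A two-sided comparison of 45% with 55% also gives 392 per arm. Read as a total, the nearest match is 10% versus 20% (or 80% versus 90%): 199 per arm, 398 in all. This does not affect the argument about kappa. It matters only for precision in step 4, where both readings are shown.

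**Assumptions.** The documents give no prevalence, error rates or cut-point. Everything below assumes a positive/negative cut on OMgrade and illustrative rates.

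**Formula.** Let π be the supervisor-positive share, and a and b the over-calls and misses as fractions of all visits. The trainee-positive share is q = π − b + a. Then Po = 1 − a − b, Pe = πq + (1 − π)(1 − q), and kappa = (Po − Pe)/(1 − Pe).

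**Step 1: a trade that kappa barely registers (π = 0.20).**
- 12 over-calls, 0 misses per 100: q = 0.32, Po = 0.88, Pe = 0.064 + 0.544 = 0.608, kappa = 0.272/0.392 = 0.694. Missed rate 0/20 = 0%.
- 0 over-calls, 8 misses per 100: q = 0.12, Po = 0.92, Pe = 0.024 + 0.704 = 0.728, kappa = 0.192/0.272 = 0.706. Missed rate 8/20 = 40%.

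**Step 2: other shares.** The number of misses that gives the same kappa as 12 over-calls is 5.8, 8.3, 9.8 and 10.9 per 100 at π = 10%, 20%, 30% and 40%. These correspond to missed rates from about 58% down to about 27%. A mixed example at π = 30%: moving from 15 over-calls and 5 misses to 5 over-calls and 12 misses keeps kappa at about 0.565. Sensitivity against the supervisor falls from 25/30 = 83% to 18/30 = 60%, and specificity rises from 55/70 = 79% to 65/70 = 93%.

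**Step 3: a strict one-for-one swap at fixed π** (over-calls 15 to 5, misses 5 to 15 per 100; raw agreement stays at 80%).

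| π | kappa | sensitivity |
|---|---|---|
| 20% | 0.474 to 0.231 | 75% to 25% |
| 30% | 0.565 to 0.474 | 83% to 50% |
| 40% | 0.600 to 0.565 | 88% to 63% |
| 50% | 0.600 to 0.600 | 90% to 70% |

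Below 50%, kappa does fall: strongly at 20%, slightly at 40%. Its value still does not say which error grew.

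**Step 4: precision of directional rates** (exams treated as independent, π = 20%).
- If 392 is the total: 196 × 0.20 ≈ 39 supervisor-positive and 157 supervisor-negative visits per arm. The 95% half-width for the between-arm difference in missed rate is 1.96 × √(2 × 0.20 × 0.80/39) = 0.178 at a 20% missed rate, and 1.96 × √(2 × 0.40 × 0.60/39) = 0.217 at 40%. For an over-call rate of 15% it is 1.96 × √(2 × 0.15 × 0.85/157) = 0.079.
- If 392 is per arm: about 78 positives per arm, and the missed-rate half-widths become 0.126 and 0.154.
- Power to detect sensitivity of 80% versus 90% is about 23% on the first reading and 42% on the second.

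**The case against.** The strongest reply is that kappa is not blind to such shifts. A reader might infer that, because kappa is unchanged when the two raters trade places, it must be unchanged when over-calls are exchanged for misses. That does not follow. Trading raters also changes the supervisor-positive share, whereas randomised weeks should have similar shares. Step 3 shows kappa falling at any fixed share below 50%. The step 1 example is also not a one-for-one swap: errors drop from 12 to 8 and raw agreement rises from 88% to 92%, and the matching number of misses depends on a prevalence that the documents do not give. All of this stands, so the claim is limited to what kappa can do, not what it always does.

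Three further inferences are tempting but unsupported.
- That the direction of trainee error is what connects Aim 1 to Aim 2. Section 2 names trainee confidence as the route to "thereby reducing frequency of antibiotic prescriptions for AOM".
- That the trial could never recover the direction. Both raters complete cards, so it could be tabulated afterwards, and the antibiotic rate is an indirect signal. The gap is in what is prespecified.
- That a miss against the supervisor is missed disease. The supervisor is a comparator, not an independent standard.

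It is also fair that kappa is not assigned to Aim 1 and that its weights are unstated; asymmetric weights would behave differently. Nothing in the plan suggests them.

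**Conclusion.** The point holds in a limited form. Aim 1 poses a directional accuracy question, and its single outcome is an agreement measure that gives no direction. Under assumed rates, the missed rate against the supervisor can go from 0% to 40% while kappa moves only from 0.69 to 0.71. The documents do not support saying that kappa will in general show no change. The conclusion rests on three readings: the supervisor as reference, kappa (with symmetric weights if weighted) as the Aim 1 statistic, and a binary cut on OMgrade for the illustrations. It is a worthwhile, low-cost improvement to the plan, not a flaw that invalidates the aim.

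**What to change.** Keep kappa, and state that it is the Aim 1 statistic and how it is weighted. Add to outcome 1A, by randomised week type:
- the proportion of paired visits in which the trainee's OMgrade is above, equal to and below the supervisor's;
- the over-call rate among supervisor-negative visits and the missed rate among supervisor-positive visits, at an OMgrade cut fixed before data are seen;
- between-arm differences with 95% intervals that allow for repeated exams by the same trainee.

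Report these as estimates beside kappa when interpreting accuracy. Do not make a claim of improvement conditional on the missed rate being no worse: without a margin such a rule cannot be applied, and step 4 shows how little precision there is to support one.

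The cost is plan wording and one table from cards already collected, for visits where both grades exist; the number of visits without a pair should be shown by week type. There are two limits. The missed-rate difference will be imprecise, at about ±18 to 22 points if 392 is the total and 20% of visits are supervisor-positive, and wider once clustering is allowed for. And because supervisors also use the device in Cellscope weeks, the reference may shift by arm. The added rates inherit that problem and do not cure it.
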